3.1.1 Statistics for BRV plasma concentrations

For BRV plasma concentration (μ g/mL) and daily dose-normalized (to 50mg) BRV plasma concentrations (Conc_{norm}, in μ g/mL), descriptive statistics include number of values, number of values above or equal to the lower limit of quantification (LLOQ), geometric mean, geometric 95% confidence interval (CI), geometric coefficient of variation (CV), arithmetic mean, SD, median, minimum, and maximum. For the calculation of descriptive statistics, a BRV plasma concentration below LLOQ is substituted by LLOQ/2.

• Conc_{norm} is derived as follows;

 $Conc_{norm} = \frac{Concentration \times 25}{Actual dose/administration (mg)}$

• Geometric $100 \times (1 - \alpha/2)$ % CI is constructed using the following formula;

$$[e^{(m-t(1-\alpha/2,n-1)\times SD/\sqrt{n})}, e^{(m+t(1-\alpha/2,n-1)\times SD/\sqrt{n})}],$$

where *m* and SD are the arithmetic mean and standard deviation of the log transformed BRV plasma concentrations for a time point, respectively. Furthermore $t(1-\alpha/2, n-1)$ is the $100 \times (1-\alpha/2)$ percentile of the t-distribution with *n*-1 degrees of freedom.

Lower and upper limits of CI are presented using significant digits same as the corresponding geometric mean.

• Geometric CV (%) is calculated using the following formula;

Brivaracetam

geometric CV(%) = $\sqrt{e^{\text{SD}^2} - 1} \times 100$,

where SD is the standard deviation from the log-transformed data.

Geometric CV (%) is presented to one decimal place.

3.2 General study level definitions

3.2.1 Analysis time points

3.2.1.1 **Relative day**

norization Relative day will be calculated as the current date minus the date of first dose of study drug for days prior to the date of first dose of study drug, and the current date minus the date of first dose of study drug plus 1 for days on or after the date of first dose of study drug and prior to or on the day of last study drug dose (eg, the day of first dose will be Day 1 and the day prior to first dose will be Day -1). For days after the last dose of study drug (including Open-Label Temporary Period), relative day will be calculated as the current date minus the date of last dose of study drug and will include a '+' to denote post-treatment days (eg, the day after the last dose will be Day +1). Relative day will not be calculated for partial dates.

3.2.2 **Study periods**

All measurements will be classified into study periods as follows

| | Baseline Period | From the date of Visit 1 prior to the date of Visit 3. |
|------|------------------------|--|
| | Treatment Period | From the date of Visit 3 until the day of Visit 7 in subjects who complete the Treatment Period; or EDV in subjects who discontinue treatment early prior to Visit 7. |
| | Ŏ | A subject is considered starting Treatment Period if the subject enters Visit 3 and is randomized. If a subject does not have a Visit 7 or EDV date, then either the date of the last scheduled or unscheduled visit during the Treatment Period or the date of last known dose of IMP during the Treatment Period, whichever is later, will define the end date of the Treatment Period. |
| | Down-Titration Period | From immediately after the last visit of the Treatment Period (Visit 7 or EDV) until Visit 8 for subjects who take any IMP during the Down-Titration Period. |
| ~ | Down-Titration Period | For subjects who enter the Down-Titration Period after the Transition Period without entering either LTFU study, MAP, or the Open-Label Temporary Period, it starts from immediately after the last visit of the Transition Period (Visit 8 Week 14). |
| THIS | Study Drug-Free Period | From immediately after the last visit of the Down-Titration Period until date of Safety Visit for subjects who enter the Down-Titration Period. |
| | Transition Period | From immediately after the last visit of the Treatment Period (Visit 7 or EDV) until Visit 8 for subjects who take any IMP |

| .3 End of treatm | nent value | |
|--------------------------------|---|---|
| Open-Label Temporary Period | This period is only applicable for subjects who cannot convert to MAP due to delayed importation of medication. The period is defined from immediately after the last visit of the Transition Period (Visit 8) and until a visit when the subject can convert to MAP. | 5 |
| | during the Transition Period and who are scheduled to enter LTFU study, MAP or Open-Label Temporary Period. | |

3.2.3 End of treatment value

The "End of treatment" value for laboratory tests, vital signs and ECG is a value collected in the last visit including unscheduled visits during the treatment period.

3.2.4 Actual stratification level per CRF

During the conduct of the randomization, some subjects with the stratification levels of LEV status or number of previous AEDs mistakenly entered to the IVRS system. The actual stratification level will be derived according to the CRF data:

The LEV status per CRF (LEV naïve vs prior LEV use) will be captured from the CRF form "History of Previous Antiepileptic Drug Treatment". Subjects will be considered with prior LEV use if levetiracetam is captured in any preferred drug name in this CRF form. Otherwise, the subjects will be considered LEV naïve.

The number of AEDs previously used but discontinued prior to study entry per CRF ($\leq 2 \text{ vs} > 2$) AEDs) will also be captured from the CRF form "History of Previous Antiepileptic Drug Treatment" by counting the number of unique AED entered in this form. However, if the same compound name is also entered in the CRF form "Prior and Concomitant Medications", the drug is not counted as a previous AED because it is considered that the subject has taken the same AED concomitantly during the study. This was instructed in the CRF completion instruction regarding how to count the number of previous AED at the randomization.

The following AEDs will be considered the same AED at the group level while counting the number of previous AEDs:

- Valproate includes valproate sodium, valproate semisodium, valproate bismuth, valproate magnesium, valpromide, ergenyl chrono, valproic acid.
- Phenytoin includes phenytoin sodium, phenytoin calcium, mephenytoin, zentronal, metetoin, ethotoin, albutoin, hydantal, phelantin, hydantol D, anirrit, dintoinale, fosphenytoin sodium, phenytoin, fosphenytoin, hydantoin derivatives, hydantoin.
- Phenobarbital includes phenobarbital sodium, methylphenobarbital, metharbital, alepsal, phenobarbital, kaneuron, epanal.
- Benzodiazepine AEDs are grouped separately by bromazepam, alprazolam, cloxazolam, diazepam group, chlordiazepoxide, clonazepam, clobazam, lorazepam, clotiazepam, temazepam, and clorazepate.

3.3 Definition of Baseline values

Baseline values will be determined from the last non-missing data collected prior to the first dose of IMP, unless otherwise noted for a specific type of data.

Baseline value for seizure frequency will be based on the 28-day adjusted seizure frequency calculated from daily record card (DRC) days over the Baseline Period. For seizures occurred on the date of Visit 3 will be entered to Visit 3 or Visit 4 CRF form "Seizure Count" depending on whether the seizure occurred before or after the randomization time. If the seizure occurred before the randomization, it would be entered to Visit 3 and counted as seizure at Baseline Period; if the seizure occurred after the randomization, it would be entered to Visit 4 and counted as seizure at Treatment Period. The calculation of 28-day adjusted frequency is described in detail in Section 3.9.3.

Baseline values for laboratory parameters, vital signs, body weight, and ECGs will be based on the latest scheduled or unscheduled assessment prior to or on the date of first administration of IMP. Baseline value will be determined separately for each individual clinical laboratory parameter for hematology, blood chemistry, and urinalysis assessments.

3.4 Important protocol deviations

Important protocol deviations (IPDs) are deviations from the protocol that could potentially impact the interpretation of the study data. The criteria for identifying IPDs and the classification of IPDs will be defined separately in the Specifications for IPDs document. To the extent feasible, rules for identifying IPDs will be defined without review of the data and without consideration of the frequency of occurrence of such deviations. Whenever possible, criteria for identifying IPDs will be implemented algorithmically to ensure consistency in the classification of IPDs across all subjects.

3.5 Analysis sets

3.5.1 Enrolled Set

The Enrolled Set (ES) consists of all screened subjects who gave informed consent (and informed assent where required). Subjects who discontinued due to screen failure are included in the ES. This analysis set is referred to as "All Subjects Screened".

3.5.2 Randomized Set

The Randomized Set (RS) consists of all subjects who were randomized to treatment.

3.5.3 Safety Set

The Safety Set (SS) will include all randomized subjects who received at least 1 dose of study medication. Safety analyses will be carried out using the SS.

3.5.4 Full Analysis Set

The Full Analysis Set (FAS) will consist of all randomized subjects who received at least 1 dose of study drug and have at least 1 post-Baseline seizure daily record card (DRC) data during the Treatment Period. Both primary and secondary efficacy analyses will primarily be carried out using the FAS.

, Stion

3.5.5 Per Protocol Set

The Per-Protocol Set (PPS) will consist of all subjects in the FAS who do not have any IPDs potentially impacting the primary efficacy variable. In order to verify the robustness of the efficacy results, the primary efficacy variable will also be analyzed using the PPS.

3.5.6 Pharmacokinetic Per Protocol Set

The Pharmacokinetic Per-Protocol Set (PK-PPS) will consist of all subjects who took at least 1 dose of BRV and for whom at least 1 valid BRV plasma concentration-time record and dosing information are available.

Treatment assignment and treatment groups 3.6

All analyses will be based on randomized treatment group. Incorrectly treated subjects will be evaluated during the blinded DEM to assess the potential impact of such cases and any special considerations for statistical analyses. In general, subjects will be analyzed according to the planned treatment dose for efficacy analyses and according to the actual treatment dose for safety and PK analyses.

The labels used in presentations will be:

3.7

, cts Not randomized All BRV (BRV 200mg/day + BRV 50mg/day) Site pooling strategy number of randomized subjects for 1 not be feasible to adjust of udy outcomes by site The number of randomized subjects for most investigator sites is expected to be low. In general, it will not be feasible to adjust statistical analyses for site effect and there are no plans to present any study outcomes by site. No site pooling strategy is defined for this study.

Coding dictionaries 3.8

Medical history and adverse events (AEs) will be coded using the Medical Dictionary for Regulatory Activities (MedDRA) version 18.1. Medications will be coded using the World Health Organization Drug Reference List (WHO-DRL) version SEP 2017. Medical procedures will not be coded.

Definitions of study-specific derived variables 3.9 Lengths of study periods 3.9.1

Number of days in Baseline Period = date of day before Visit 3 - date of Visit 1.

Note that the 0.5 day is attributed from the day of Visit 3 which is considered part of the Baseline Period, and 0.5 days from the day of Visit 1 which is also considered part of the **Baseline** Period

Number of days in Treatment Period = date of Visit 7 (or EDV) – date of Visit 3.

Note that the first and last day of treatment period are considered as half days.

A similar calculation formula to the Treatment Period is applied to other post-treatment periods.

Lach seizure code in the clinical database will be mapped to exactly 1 of the following codes based on the International League Against Epilepsy (ILAE) classification (1981): IA (IA1, IA2, IA3, and IA4), IB, IC, II (IIA, IIB, IIC, IID, IIE, and IIF) or III. With regard to cluster seizures. investigate

rather than reporting the estimated number of individual seizures. Therefore, no imputation will . be applied for the seizure counts corresponding to reports of cluster seizures. Namely, in all the efficacy analyses, each cluster episode will be counted as one seizure of reported seizure type.

The total number of seizures for seizure type I (IA+IB+IC) and the total number of seizures for all seizure types (I+II+III) will be calculated across all DRC data over the study period being summarized.

28-day adjusted seizure frequency and log-transformed seizure 3.9.3 frequency

Twenty-eight day adjusted seizure frequency for partial seizures (seizure types IA+IB+IC), and for all seizure types (I+II+III) will be calculated for each study period by dividing the number of targeted seizures (partial seizures or all seizure types) by the number of days for which the DRC was completed for each study period, and multiplying the resulting value by 28.

The above values for each study period will be transformed using the function log(x+1), where log represents the natural logarithm function.

Seizure freedom during the Treatment Period 3.9.4

Seizure freedom is assessed for partial seizures and all epileptic seizures.

All epileptic seizures freedom 3.9.4.1

Subjects are defined as all epileptic seizure-free during the Treatment Period if they meet all of the following criteria.

- 1. The subject completed the Treatment Period, and
- 2. The subject did not have any missing days in the DRC over the Treatment Period, and
- 3. The subject did not report any seizures over the Treatment Period

Specific algorithmic rules for each of the above are defined as follows:

Criterion 1: A subject is defined as completing the Treatment Period if the subject completed all scheduled visits of Treatment Period (ie, Visit 4 to Visit 7).

Criterion 2: A subject meets criterion 2 if no "Not Done" dates were reported from Visit 4 up to Visit 7 in the Seizure Counts CRF module.

Note that the CRF module for Visit 4 covers seizure records from the afternoon at the date of Visit 3 up to the morning at the date of Visit 4, and that the module for Visit 7 covers seizure records from the afternoon at the date of Visit 6 up to the morning at the date of Visit 7.

121101 Criterion 3: A subject meets criterion 3 if there are no records of seizures from Visit 4 up to Visit 7 in the Seizure Counts CRF module with either a count >0 or a reported seizure code with an unknown or missing seizure count.

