7 MEASUREMENTS OF TREATMENT COMPLIANCE

IMP compliance (%) will be calculated according to the definition shown in the formula below;

Compliance(%) =
$$100 \times \frac{\text{Number of tablets taken}}{\text{Number of tablets that should have been taken}}$$

In general, for a duration where the number of tablets which should be taken per day is constant, the compliance is represented as follows;

Compliance(%) =
$$100 \times \frac{(\text{Number of tablets dispensed}) - (\text{Number of tablets returned})}{(\text{Number of tablets per day}) \times (\text{Number of days in the duration})}$$

If a period where the number of tablets which should be taken per day may not be constant, the compliance will be calculated as a weighted sum of compliance of each duration weighted by length of the duration.

Compliance(%) =
$$100 \times \sum_{i} (C_i \times W_i)$$
,

where *i* represents a duration with a constant number of tablets per day,

(Number of tablets dispensed for *i*)-(Number of tablets returned for *i*)

$$C_i = \frac{1}{(\text{Number of tablets per day for } i) \times [(\text{End date of } i) - (\text{Start date of } i)]'}$$

$$W_i = \frac{(\text{End date of } i) - (\text{Start date of } i)}{(\text{End date of Period}) - (\text{Start date of Period})^2}$$

Note that the first and last day of treatment are considered as half days because the start day of each duration will contribute evening only and the last day of it will contribute morning only.

For a period where treatment is double-blind, the number of tablets which should been taken per day is defined in Table 3.1, Table 3.2 and Table 3.3.

For instance, total planned tablet number during the Treatment Period will be calculated as 6 times the number of days from the first dose of IMP (Visit 3) up to the last visit in the period (EDV for early discontinuers, Visit 7 otherwise).

Brivaracetam

Compliance for Treatment Period (%)

$$= 100 \times \frac{(\text{Number of tablets dispensed}) - (\text{Number of tablets returned})}{6 \times [(\text{Date of EDV or Visit 7}) - (\text{Date of Visit 3})]}$$

orization For the overall compliance which consists of the Treatment Period and either the Transition Period or the Down-Titration Period, the denominator of the formula for W_i is represented as [(the latest date of EDV, Visit 7 and Visit 8) – (Date of Visit 3)].

For the Open-Label Temporary Period,
$$C_i$$
 can be applied for the above formula as only BRV
25mg tablet will be used.

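### The Baseline length formula in SAP 3.9.1 gives 55 days for an 8-week baseline, one day short of its own half-day note and the parallel Treatment formula

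*SAP*

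**What the plan says.** SAP 3.9.1 defines the Baseline length as "Number of days in Baseline Period = date of day before Visit 3 - date of Visit 1". The note directly beneath says that "the 0.5 day is attributed from the day of Visit 3 which is considered part of the" Baseline Period, and assigns another half day to Visit 1. For the Treatment Period the same section takes the date of Visit 7 (or the early discontinuation visit) minus the date of Visit 3, and adds: "Note that the first and last day of treatment period are considered as half days".

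Other passages bear on the same length:
- SAP 3.2.2 defines the Baseline Period as "From the date of Visit 1 prior to the date of Visit 3".
- SAP 3.3 says of a seizure on the Visit 3 date before randomization that "it would be entered to Visit 3 and counted as seizure at Baseline Period".
- SAP 7 uses Visit 7 minus Visit 3 in the compliance denominator, with nothing added, because "the first and last day of treatment are considered as half days".

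For the 28-day frequency, SAP 3.9.3 divides the seizure count "by the number of days for which the DRC was completed for each study period". SAP 3.3 describes the Baseline value as "calculated from daily record card (DRC) days over the Baseline Period". SAP 4.2 and Protocol 13.6 likewise refer to non-missing diary days. SAP 8.1.1 nevertheless names 3.9.1, together with 3.9.2 and 3.9.3, as the place where the standardized frequency calculation is detailed.

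**The concern.** The printed equation subtracts a day that the note puts back. A programmer who follows the equation gets a different Baseline length from one who follows the note, and the section does not say which governs. Because SAP 8.1.1 cites 3.9.1 for the primary variable, the length could end up in the denominator of Baseline seizure frequency, for example as period length minus missing diary days.

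Baseline frequency would then be slightly too high for everyone. Percent reduction from Baseline (SAP 8.2.1), 50% response (8.2.2) and the reduction categories (8.2.3) would all shift slightly in the favourable direction in every arm, placebo included. The numerator and denominator would also disagree: Baseline seizures are counted into part of the Visit 3 date, and the printed length does not cover that time.

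**Working it through.** **Inputs.** The Baseline Period is 8 weeks and the Treatment Period 12 weeks (SAP 2.3.1). Put Visit 1 (V1) at day 0, Visit 3 (V3) at day 56 and Visit 7 (V7) at day 140. Visits may move by ±3 days.

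**Length of the Baseline Period**

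| Source | Calculation | Days |
|---|---|---|
| 3.9.1 equation as printed | (V3 − 1) − V1 = 55 − 0 | 55 |
| 3.9.1 note, half a day at each end | 0.5 + 55 full days + 0.5 | 56 |
| Treatment-type formula applied to Baseline | V3 − V1 | 56 |
| 3.2.2, whole dates from V1 up to but not including V3 | days 0 to 55 | 56 |
| Planned length | 8 × 7 | 56 |

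The Treatment formula agrees with its own note: V7 − V3 = 84 = 0.5 + 83 + 0.5. Taken together, the two 3.9.1 formulas give 55 + 84 = 139 days from Visit 1 to Visit 7, against 140 on the calendar. The shortfall is exactly one day for any visit dates, since (V3 − V1) − [(V3 − 1) − V1] = 1.

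**Effect on Baseline frequency.** If completed DRC days are counted directly from the diary, the effect is 0. If they are derived as the 3.9.1 length minus m missing days, Baseline frequency is multiplied by (L − m)/(L − 1 − m), where L is the true length. The five-missing-day column is an assumed scenario, not a figure from the plan.

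| L | m = 0 | m = 5 |
|---|---|---|
| 53 | 53/52 = 1.019 | 48/47 = 1.021 |
| 56 | 56/55 = 1.018 | 51/50 = 1.020 |
| 59 | 59/58 = 1.017 | 54/53 = 1.019 |

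Example: 8 baseline seizures give 8/56 × 28 = 4.00 per 28 days, but 8/55 × 28 = 4.07 with the printed length.

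**Effect on percent reduction.** With true reduction r, the reading is 1 − (1 − r) × 55/56 for a complete diary, and 1 − (1 − r) × 50/51 with five missing days.
- True 0% reads 1.8% (2.0% with five missing days).
- True 25% reads 26.3% (26.5%).
- The 50% cut is met at a true 1 − 0.5 × 56/55 = 49.1% (1 − 0.5 × 51/50 = 49.0%).

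**First change of 50% responder status.** This is the smallest baseline count, searching upward from the eligibility minimum of 8 seizures with an 84-day treatment diary, at which any treatment count changes the classification.
- Complete baseline diary: 21 baseline and 16 treatment seizures. Treatment frequency is 16/84 × 28 = 5.33. Baseline is 10.50 with 56 days (reduction 49.2%, non-responder) or 10.69 with 55 days (50.1%, responder).
- Five missing baseline days: 12 baseline and 10 treatment seizures. The true reduction of 49.4% reads 50.4%.

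**Effect on the primary ANCOVA.** The Baseline covariate log(x + 1) rises by 0.014 at x = 4 and 0.018 at x = 50 seizures per 28 days (0.016 and 0.019 with five missing days). The shift is nearly constant and the same in all arms, so the intercept absorbs almost all of it. In a simulation with assumed log-normal seizure rates (148 per arm, effects −0.221 and −0.285 on the log scale, 300 runs), the treatment contrast moved by at most 0.0001.

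**The case against.** The strongest reply is that the stated denominator is not this length. SAP 3.9.3, 3.3 and 4.2 and Protocol 13.6 all speak of diary days. The only link to 3.9.1 is the list of sections in 8.1.1, which may be there simply for the period boundaries. On that reading nothing changes. This stands as a limit on the reach of the error. It does not remove the error, because no passage says how completed diary days are counted. SAP 3.9.4.1 shows that missing days are recorded as dates, at least for the Treatment Period visits, so length minus missing days would be a natural way to program the count.

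A second reply is that the note can be read as adding one day to the printed 55, so the section as a whole means 56. That is fair as to intent, but it confirms that the equation alone does not state the intended length.

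Third, the text around SAP 3.9.1 is visibly damaged by extraction, and the note refers to the half day as though such a term had already appeared. A lost term on the original page cannot be excluded. The formula line itself does read as a complete sentence.

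Fourth, SAP 3.2.2 reaches 56 by whole calendar dates and leaves Visit 3 out, so it supports the total but not the half-day convention. That is correct. The main support is the note and the Treatment formula.

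Finally, no decision turns on this. Eligibility uses raw counts, the affected variables are secondary and tested at a nominal level, and SAP 4.2 expects good diary compliance. That is accepted.

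**Conclusion.** The concern holds. As printed, the Baseline length in SAP 3.9.1 is one day short of what the section itself intends: 55 days against 56 for an 8-week baseline. The consequence is nil if DRC days are counted directly. It is about 2% in Baseline frequency, equally in all arms, if they are derived from the 3.9.1 length; the documents do not establish which applies. In the second case a few subjects just below 50% reduction could be classed as responders, and the other category boundaries are exposed in the same way. The primary between-arm contrast and eligibility are not materially affected.

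This is an optional correction. Confidence is medium because a term may have been lost from the page. The size figures rest on an 84-day treatment diary, on either a complete baseline diary or an assumed five missing days, and, for the simulated contrast, on assumed seizure rates.

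**What to change.** First check the original SAP page for a lost term. If the formula is as printed, define the number of Baseline days as the date of Visit 3 minus the date of Visit 1, with half a day at each end, as for the Treatment Period. Then settle the cross-reference: either say in SAP 3.9.3 that completed DRC days are derived from the 3.9.1 length, and how missing days are deducted, or remove 3.9.1 from the list in SAP 8.1.1.

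The cost is one line of SAP text, one cross-reference and at most one line of derivation code. If the 55-day length had already been programmed, reported reductions from Baseline would become very slightly smaller in every arm.

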### Early Discontinuation Visit (after randomization) 8.8

Assessments for subjects that discontinue the study early are as follows: SU

- Vital signs •
- Body weight •
- Physical examination •
- Neurological examination
- Psychiatric and mental status
- ECG
- **IVRS/IWRS**
- Subject DRC dispensed
- Subject DRC returned and reviewed
- Seizure counts
- Laboratory safety assessments
- Pregnancy test (urine)

- BRV plasma level •
- AE reporting

- •

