3.9.4.2 Partial seizures freedom

Criteria 1 and 2 (see Section 3.9.4.1) are the same as for all epileptic seizure freedom. However, criterion 3 is modified to only include partial seizures.

3. The subject did not report any partial seizures over the Treatment Period

Criterion 3: A subject meets criterion 3 if there are no records of partial seizures from Visit 4 up to Visit 7 in the Seizure Counts CRF module with either a partial seizure frequency count >0 or a reported partial seizure code with an unknown or missing seizure count.

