8.2.4 Seizure freedom (partial, all epileptic seizure)

Seizure freedom will be assessed separately for partial seizure and for all epileptic seizure.

12til01 A subject is defined as all epileptic seizure free over the Treatment Period if they meet all of the following criteria.

- 1. The subject completed the Treatment Period
- 2. The subject did not have any missing days in the DRC during the Treatment Period, and
- 3. The subject did not report any seizures during the Treatment Period

The algorithm rules for all epileptic seizure freedom are described in Section

The number and percentage of subjects who are seizure free for partial seizure and for all seizure types over the Treatment Period will be summarized.

Additionally, the number and percentage of subjects who met each individual criterion will be summarized, irrespective of whether the other criteria were met. Furthermore, the number and percentage of subjects meeting criteria 2 and 3 but not meeting criterion 1 (ie, subjects without seizures and without missing days in the DRC but discontinued) will be summarized.

Seizure freedom rates for all seizure types will be compared between each BRV treatment group and PBO using Fisher's Exact Test.

The analysis above will be repeated for partial seizure instead of all epileptic seizure (also refer to Section 3.9.4.2).

Seizure frequency for all seizure types 8.2.5

Estimates of percent reduction over PBO and odds ratios for 50% responder rates and corresponding two-sided 95% CIs for seizure frequency for all seizure types (I+II+III) will be provided based on the statistical methodology described in Section 8.1.1, Section 8.1.2 and Section 8.2.2. Additionally, percent reduction from Baseline in seizure frequency for all seizure types will be analyzed as described in Section 8.2.1. Statistical treatment group comparisons will also be provided as described in these sections. In addition, seizure frequency will be listed by subject, study period and seizure type. The data from the DRC will also be listed by subject and study period.

Time to nth partial seizure 8.2.6

The algorithm rules for time to n^{th} partial seizure are described in Section 3.9.5.

Median time to n^{th} seizure and corresponding 95% CIs will be provided based on Kaplan–Meier (KM) estimation. KM plots will be provided for time to n^{th} partial seizure (n=1, 5, 10).

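### Criteria 2 and 3 for seizure freedom leave out the Early Discontinuation Visit, so some descriptive counts in SAP 8.2.4 can show discontinuers as having no seizures and a complete diary

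*SAP*

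**What the plan says.** SAP 3.9.4.1 defines freedom from all seizures by three joint criteria: "Subjects are defined as all epileptic seizure-free during the Treatment Period if they meet all of the following criteria". In words, these are completion of the Treatment Period, no missing diary days over it, and no reported seizures over it. Each then receives an algorithmic rule:

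- Criterion 1 reads: "A subject is defined as completing the Treatment Period if the subject completed all scheduled visits of Treatment Period (ie, Visit 4 to Visit 7".
- The rule for criterion 2 is met when no 'Not Done' "dates were reported from Visit 4 up to" Visit 7 in the Seizure Counts module.
- Criterion 3: met "if there are no records of seizures from Visit 4 up to Visit 7 in the Seizure Counts CRF module" with a positive count, or with a seizure code whose count is unknown or missing.

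For partial seizures, SAP 3.9.4.2 keeps criteria 1 and 2 and repeats the visit limits in criterion 3: "A subject meets criterion 3 if there are no records of partial seizures from Visit 4 up" to Visit 7.

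SAP 3.2.2 ends the Treatment Period at Visit 7 for completers, or at the "EDV in subjects who discontinue treatment early prior to Visit 7". SAP 3.9.1 measures its length the same way. At the EDV, Protocol 8.8 lists "Subject DRC returned and reviewed" and also seizure counts; Protocol Table 5-1 agrees.

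SAP 8.2.4 plans more than the seizure-freedom rate. It tabulates each criterion on its own, regardless of the other two. It also counts subjects who meet criteria 2 and 3 but not 1, described as "subjects without seizures and without missing days in the DRC but discontinued". All of this is repeated for partial seizures.

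**The concern.** The worded criteria cover the whole Treatment Period, but the operative rules cover only the modules for Visits 4 to 7. For a completer the two agree. For a discontinuer they differ by the last diary interval, which runs from the last regular visit attended to the EDV.

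Both rules are also satisfied by the absence of records. A subject who stops before Visit 4 has no Visit 4 to 7 module, and so passes criteria 2 and 3 whatever the EDV diary shows.

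The count of criteria 2 and 3 without 1 is made up entirely of non-completers, the group whose final diary interval is skipped. A reader would take it as the number of patients who were doing well and left for other reasons. Some of them may have had seizures, or unrecorded days, shortly before leaving. What is at stake is the accuracy of that count and of the stand-alone counts for criteria 2 and 3.

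**Working it through.** The plan gives no figure on this point to reproduce, so the check is mainly one of logic.

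**Step 1: apply the rules to constructed subjects.** In these cases only the seizure rule (criterion 3) varies; criterion 2 is taken as met. The last two columns show whether the subject enters the count of criteria 2 and 3 but not 1.

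| Subject | Criterion 1 | Criterion 3 as written | Seizure-free (all three) | In count, as written | In count, EDV included |
|---|---|---|---|---|---|
| A: completer, no seizures | yes | yes | yes | no | no |
| B: EDV on Day 10, 3 seizures recorded at EDV | no | yes (no module to check) | no | yes | no |
| C: Visits 4 and 5 clean, then 2 seizures at EDV | no | yes | no | yes | no |
| D: 1 seizure at Visit 4, then EDV | no | no | no | no | no |
| E: Visits 4 to 6 clean, then 2 seizures at EDV | no | yes | no | yes | no |

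B, C and E enter the count wrongly, and including the EDV removes all three. D is handled correctly already. The column for all three criteria is the same under either rule. Criterion 2 has the same gap: a 'Not Done' day recorded only at the EDV is not looked at.

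**Step 2: compare with the rest of the SAP.** For discontinuers, SAP 4.2 computes seizure frequency from diary data up to the last visit of the Treatment Period. SAP 3.9.5 does the same for time to nth seizure and includes that last visit. Section 7 names the EDV in the compliance formula. Subject B would therefore have a non-zero primary frequency and an event for time to first seizure, yet be described in SAP 8.2.4 as having had no seizures.

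**Step 3: illustrate how often an unchecked interval contains a seizure.** Inclusion criterion 9 requires at least 8 partial seizures in 8 weeks, so the entry minimum is 8/8 = 1 per week. Assume a Poisson process with rate r per week over w weeks: P(at least one) = 1 − exp(−r × w). Visits at Weeks 2, 4, 8 and 12 make the nominal interval at most 2 weeks up to Week 4 and at most 4 weeks after that.

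| Assumed on-treatment rate per week | 1 week | 2 weeks | 4 weeks |
|---|---|---|---|
| 1.0 (entry minimum, no improvement) | 63% | 86% | 98% |
| 0.5 | 39% | 63% | 86% |
| 0.25 | 22% | 39% | 63% |

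For a subject who stops before Visit 4, this is the chance of being wrongly shown as without seizures. A later discontinuer must also have had no seizure in the modules that are checked. At 1 per week, the chance of that is exp(−2) = 14% up to Week 2 and exp(−4) = 2% up to Week 4. At that rate, misdescription would come mostly from very early stops.

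**The case against.** The strongest reply is that the intention is already clear. The worded criteria refer to the Treatment Period, which ends at the EDV for a discontinuer, so a programmer might include the EDV anyway. But the SAP presents the Visit 4 to 7 rules as the specific algorithm, and a program would follow those. The wording conflicts with the algorithm and does not override it.

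Second, SAP 5.1.3 remaps an EDV before Visit 7 to the next scheduled visit. If this also governed the Seizure Counts data, the gap in criteria 2 and 3 would close. However, the rule is given for counts of subjects completing each visit, and section 3.9.4 does not refer to it. Applying it here would raise another question: an EDV after Visit 6 would become Visit 7 and might be read as meeting criterion 1. Either reading needs a clarifying sentence.

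Third, the CRF is not in the documents, so it is an inference from Protocol Table 5-1 and 8.8 that EDV counts are stored outside the Visit 4 to 7 modules. That caveat stands. SAP 3.9.4.1 does describe the modules by the interval ending at a named visit, which supports the inference. The limits could instead be read as a time span that includes any EDV between Visits 4 and 7, but an EDV before Visit 4 would still fall outside it.

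Fourth, the affected counts are descriptive, and SAP 8.2.5 lists diary data and seizure frequency by subject, so a misplaced subject could be found. This stands and limits the severity.

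**Conclusion.** The point holds as a minor inconsistency with a definite but narrow effect. Read literally, criteria 2 and 3 omit a discontinuer's final diary interval. The affected SAP 8.2.4 outputs are criterion 2 alone, criterion 3 alone, and criteria 2 and 3 without 1. The conclusion assumes that EDV seizure counts are not filed under a Visit 4 to 7 module.

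A reader might infer three stronger claims that the documents do not support:

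- *Discontinuers are counted as seizure-free in the tested comparison.* They are not. All three criteria are required, criterion 1 requires Visits 4 to 7, and Protocol 13.3.2 also requires completion. The seizure-freedom rate and Fisher's test are unaffected. The primary and time-to-nth-seizure analyses use data up to the last Treatment Period visit and are also unaffected.
- *The count is inflated by a known factor.* The number affected depends on how many subjects discontinue and when, and the documents give neither. The percentages above are conditional on an assumed rate and are illustrations only.
- *The error favours one arm.* That would need differential early dropout. SAP 4.2 reports low dropout in earlier studies with no clear dose-response, and Protocol 2.4 describes discontinuation as similar to placebo.

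**What to change.** In SAP 3.9.4.1 and 3.9.4.2:

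1. Define criteria 2 and 3 over all Seizure Counts records of the Treatment Period, up to and including Visit 7 or the EDV.
2. State that criterion 2 fails if the diary is absent for any day up to that visit, so that a missing module cannot count as a pass.
3. State that criterion 1 requires an actual Visit 7, and that an EDV remapped to Visit 7 under SAP 5.1.3 does not qualify.

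The cost is a few sentences in the SAP and a small program change. No new data are needed, and sample size, power and the tested comparisons stay as they are.
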